12.4.4 Handling of missing values not related to intercurrent event

Imputation of missing values will be done following the Last Observation Carried Forward (LOCF) method mainly for the secondary endpoints. An observed approach will be also considered.

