12.4.5 Sensitivity analyses for primary endpoint/estimand

A sensitivity analysis on the primary model will be performed using the LOCF approach in case of missing SD-OCT or OCTA evaluations between Week 4 and Week 16.

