Based on the study protocol, the primary endpoint should be analyzed according to Recursive Partitioning and Amalgamation (RECPAM) classification-tree analysis followed by multivariable logistic regression model. The RECPAM procedure was specified to evaluate interactions between imaging measurements assessed by OCT, OCTA, FA, ICGA and CFP and to identify distinct and homogeneous subgroups of participants in terms of q12w fluid-free participants at Week 48. This procedure should also have the aim to select the variables to be included in the multivariable logistic regression model and how to include them (for continuous, a threshold is identified during RECPAM). Based on data analyzed for the planned interim analysis, the image's grading of SD-OCT and mainly OCTA was affected by many ungradable values due to image's quality or due to pathology providing a great number of missing data that in RECPAM procedure cannot be managed. Moreover, the initial planned number of 263 enrolled patients wasn't reached, and the final number of 122 enrolled patient is too small for this type of the analysis. For these reasons, the RECPAM procedure will not be performed and in section 6.3.1 a different method to consider these variables in the multivariable logistic regression model and to choose them will be planned and explained. Moreover, the primary outcome will be considered as 'failure' also for patients who discontinued treatment during the study since for these patients the maintenance of a stable q12w regimen assigned at Week 16 up to Week 48 can not be observed and, thus, also these cases, will be considered as intercurrent event.

Moreover, in the primary analysis OCTA assessments planned in the study protocol will not be considered since based on interim analysis, it was observed that for these parameters most values will be missing.

| | |
|--|----------------------------------|
| | Statistical Analysis Plan |
| | Sponsor: Novartis |

Protocol: CRTH258AIT04

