For what concern the LOCF approach reported in the study protocol, this approach will be maintained for the predictors to be included in the analysis of the primary endpoint since the focus is on the first visits (from baseline to Week 16) and all enrolled patients should perform these visits independently of treatment regimen that will be followed by each patient. For the secondary endpoints, LOCF approach will not be applied because after Week 16 each patient will have different scheduled of visits based on treatment regimen. The LOCF approach can be considered only until Week 16 but (1) for OCTA the number of missing data will lead to most data imputed than the one observed, (2) for SD-OCT the approach is applied in the analysis of primary endpoint, (3) for BCVA the LOCF approach will be provided until Week 16, (4) for HAD and EQ-5D-5L questionnaires the LOCF approach will not be applied since only two assessments of these questionnaires are planned in the study.

As performed for interim analysis, all analysis will be conducted on Safety population since during the interim analysis, in which all enrolled patients were considered (see section 6.6 for further details), the FAS and Safety populations include the same set of patients since per definitions of the study protocol, the FAS considered all enrolled patients who completed the baseline visit and all of them are treated and consequently all of them belong to Safety population.

The evaluation of prevalence of anxiety and depression will be performed only based on HAD questionnaire and not based in terms of treatment that patients could have received for anxiety/depression.

The following additional analysis will be included:

- SD-OCT parameters at baseline and type of predominant lesion will be also analyzed according to BCVA groups and CST groups based on changes at Week 12 in patients who performed Week 16 and were still on treatment at this timepoint.
- A graphical representation of BCVA ETDRS score and CST by means of spaghetti plot will be provided.
- Analyses on CST and BCVA will be also performed on patients with BCVA ETDRS score lower than 69 letters at baseline.

| | |
|--|----------------------------------|
| | Statistical Analysis Plan |
| | Sponsor: Novartis |
| | Protocol: CRTH258AIT04 |

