6.3. Efficacy Evaluation

6.3.1. Primary efficacy analysis

Definition of primary endpoint

The primary aim of the study is to assess which early anatomical parameters measured by multimodal imaging at each visit from Baseline to Week 16, predict in brolucizumab-treated participants with wAMD the q12w fluid-free response at Week 48.

The primary estimand of the study is to identify the q12w fluid-free predictive factors.

Patient will be classified as follows for the outcome of interest:

- **q12w fluid-free:** patients completing the treatment and the study maintaining a stable q12w regimen assigned at Week 16 up to Week 48 and without the presence of IRF and SRF at Week 48 according to SD-OCT grading.
- **not q12w fluid-free:**
 - patient who completes the treatment and the study with the presence of IRF or the presence of SRF at Week 48 according to SD-OCT grading;
 - patient who followed the q8w regimen of treatment at any time during the study (considering also who started with q12w regimen but then due to disease activity shifted to q8w regimen);
 - patient who discontinued treatment at any time after baseline since also the discontinuation from the treatment can be considered as intercurrent event and according to data handling rules should be considered as 'failure'.
 - patient who dropped out at any time after baseline since the discontinuation from the study is considered as intercurrent event and according to data handling rules should be considered as 'failure'.

The following qualitative and quantitative anatomical parameters measured by FA, ICGA, CFP and SD-OCT will be considered as potential predictive factors in the statistical model and, when measured at more than one timepoint, categories variables based on their changes between baseline and Week 16 will be created as described below:

| | |
|--|---|
| | Statistical Analysis Plan |
| | Sponsor: Novartis Protocol: CRTH258AIT04 |

| Variable | Timing of data collection | Source | Categories used in the model | Reference value for the model |
|----------------------------------|---|--|--|-------------------------------|
| Type of predominant CNV lesion | Screening | CRC grading based on SD-OCT, FA, ICGA and CFP at Screening | Type I, Type II, Type III, PCV, UNG/P or UNG/Q. Of note, Type I and PCV will be considered as unique category while UNG/P and UNG/Q will be considered as missing data. | Type I + PCV |

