| subRPE fluid | Baseline, Week 4, Week 8, Week 12 and Week 16 | SD-OCT grading | Stable absent (i.e., all measurement 'No'), Stable present (i.e., all measurement 'Yes'), Improved (i.e., last measurement collected as 'No' and baseline 'Yes'), Worsened (i.e., last measurement collected 'Yes' and baseline 'No'). | Stable absent |
| SHRM | Baseline, Week 4, Week 8, Week 12 and Week 16 | SD-OCT grading | Stable absent (i.e., all measurement 'No'), Stable present (i.e., all measurement 'Yes'), Improved (i.e., last measurement collected as 'No' and baseline 'Yes'), Worsened (i.e., last measurement collected 'Yes' and baseline 'No'). | Stable absent |
| ORT | Baseline, Week 4, Week 8, Week 12 and Week 16 | SD-OCT grading | Stable absent (i.e., all measurement 'No'), Stable present (i.e., all measurement 'Yes'), Improved (i.e., last measurement collected as 'No' and baseline 'Yes'), Worsened (i.e., last measurement collected 'Yes' and baseline 'No'). | Stable absent |
| ELM integrity loss in center 1mm | Baseline, Week 4, Week 8, | SD-OCT grading | Stable absent (i.e., all measurement 'No'), Stable present (i.e., all measurement | Stable absent |

| | |
|--|----------------------------------|
| | Statistical Analysis Plan |
| | Sponsor: Novartis |
| | Protocol: CRTH258AIT04 |

| | | | | |
|-------------|---|----------------|--|---------------------------|
| | Week 12 and Week 16 | | 'Yes'), Improved (i.e., last measurement collected as 'No' and baseline 'Yes'), Worsened (i.e., last measurement collected 'Yes' and baseline 'No'). | |
| Type of PED | Baseline, Week 4, Week 8, Week 12 and Week 16 | SD-OCT grading | Stable Fibrovascular only (i.e. all measurement 'Fibrovascular only'), Stable not only fibrovascular (i.e. all measurement 'Predominantly fibrovascular' or 'Predominantly serous' or 'Drusenoid PED'), 'From Fibrovascular only to not only fibrovascular' (i.e., last measurement collected 'Predominantly fibrovascular' or 'Predominantly serous' or 'Drusenoid PED' and baseline 'Fibrovascular only'),), 'From not only fibrovascular to Fibrovascular only' (i.e., last measurement collected 'Fibrovascular only' and baseline 'Predominantly fibrovascular' or 'Predominantly serous' or 'Drusenoid PED'). | Stable Fibrovascular only |
| CST (μm) | Baseline, Week 4, Week 8, Week 12 and Week 16 | SD-OCT grading | Percentage changes in CST vs baseline at the last measurement collected. | NA |

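### Carrying an earlier SD-OCT scan forward to Week 16 moved from a protocol sensitivity analysis to the SAP's only rule for the primary predictors, and no planned analysis shows its effect

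*SAP*

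**What the plan says.** **Protocol.** Section 12.4.5 states: "A sensitivity analysis on the primary model will be performed using the LOCF approach in case of missing SD-OCT or OCTA evaluations", for the period Week 4 to Week 16. Section 12.4.4 describes LOCF as a "method mainly for the secondary endpoints. An observed approach will be also considered". No section states outright how the primary model treats a missing predictor. Section 12.4.7 speaks of restoring a complete-case analysis to its original sample, which implies that the primary model uses complete cases.

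**SAP.** Section 1.1, which lists changes from the protocol, says of LOCF that "this approach will be maintained for the predictors to be included in the analysis of the primary endpoint", and adds that "for SD-OCT the approach is applied in the analysis of primary endpoint". Section 6.3.1 introduces the repeated predictors with "categories variables based on their changes between baseline and Week 16 will be created as described below". The table beneath it takes the follow-up value from the last scan collected. For CST the entry is "Percentage changes in CST vs baseline at the last measurement collected". The Improved and Worsened categories (sub-RPE fluid, SHRM, ORT, ELM loss) and the two PED-change categories follow the same rule. The Stable categories use all measurements.

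The one sensitivity analysis left in SAP 6.3.1 weights completers by the inverse of a modelled missingness probability. The outcome of that weighting model is study drop-out, and the weighted model keeps the covariates already selected.

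On data quality, SAP 1.1 reports: "grading of SD-OCT and mainly OCTA was affected by many ungradable values due to" image quality or pathology. It gives no rate by visit or modality.

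**The concern.** LOCF has changed role. A sensitivity analysis on LOCF makes sense only if the primary model does not use it. The SAP puts LOCF in the primary models and leaves nothing beside it, so the comparison that the protocol planned has gone. A reader of SAP 1.1 would take the word used there to mean that nothing had changed.

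The carried value also does not measure what the predictor is said to measure. Week 16 is the first visit at which disease activity is assessed and the regimen chosen, and the outcome requires the q12w regimen assigned at that visit to be kept. An eye that looks better at Week 12 and worsens by Week 16, with an ungradable Week 16 scan, is labelled Improved. At stake is whether the odds ratios describe change to Week 16, or a mixture of that and an earlier point in the injection cycle, in a proportion that the plan does not report.

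**Working it through.** **1. Timing.** Injections are at Baseline, Week 4 and Week 8 (Protocol 3). Week 12 has no injection, and scans precede dosing (Protocol 8.3). Nominal weeks since the previous injection are:

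| Scan | Previous injection | Weeks since |
|---|---|---|
| Week 4 | Baseline | 4 − 0 = 4 |
| Week 8 | Week 4 | 8 − 4 = 4 |
| Week 12 | Week 8 | 12 − 8 = 4 |
| Week 16 | Week 8 | 16 − 8 = 8 |

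Any carried post-baseline scan is therefore a 4-week scan standing in for an 8-week scan.

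**2. Does another planned analysis test the carried values?** The drop-out weighting does not. An eye on study with an ungraded Week 16 scan is not a drop-out, and it still has a last measurement, so it is not excluded as missing a covariate. The by-visit image-quality tables (SAP 6.3.2.2) show how often scans could not be graded, but give no odds ratio without carried values. For BCVA, a secondary endpoint, SAP 6.3.2.3 runs observed and LOCF analyses side by side to Week 16. The primary predictors have no such pair.

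**3. Possible size.** The documents give no figure for this point, so there is none to reproduce. The inputs below are assumptions.

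- Week 16 value x is standard normal, and logit P(response) = ln(2)·x, so the true odds ratio is 2.0 per SD.
- Earlier scan w = ρ·x + √(1 − ρ²)·e + shift, with e standard normal, ρ = 0.5, 0.7 or 0.9, and shift 0, 0.5 or 1 SD in the favourable direction.
- In a share of eyes x is replaced by w. A one-variable logistic model is then fitted, with 400,000 simulated eyes per scenario.

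| Share carried | Odds ratio under LOCF |
|---|---|
| 10%, unrelated to outcome | 1.80–1.99 |
| 20%, unrelated to outcome | 1.67–1.96 |
| 15% of non-responders, 5% of responders | 1.63–1.98 |
| 30% of non-responders, 10% of responders | 1.40–1.97 |
| 15% of responders, 5% of non-responders | 1.91–2.08 |
| 30% of responders, 10% of non-responders | 1.85–2.16 |

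Observed-only models returned about 2.0 throughout, but in these scenarios missingness depended on outcome only.

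**4. Cost of observed-only.** The number of eyes is 122 × (1 − m), and the standard error grows by 1/√(1 − m).

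- m = 10%: 122 × 0.90 ≈ 110 eyes; 1/√0.90 = 1.054, about 5% larger.
- m = 20%: 122 × 0.80 ≈ 98 eyes; 1/√0.80 = 1.118, about 12% larger.

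**The case against.** **The odds ratios are not shown to be diluted.** A reader might infer that they are, but the table in the working runs from 1.40 to 2.16, and the direction depends on which eyes lack a Week 16 scan. The simulation also lets the Week 16 value alone drive the outcome. If a stable trait of the eye drove it and the two scans were exchangeable, carrying a value would leave the odds ratio unchanged. Dilution would return only with a mean shift. The simulation speaks directly to CST; the other five repeated predictors are categorical. All of this stands.

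**Observed-only models need not find more predictors.** A reader might expect them to. In simulations of 122 eyes at correlation 0.8, LOCF passed the p<0.10 screen in 95.5–97.1% of runs with 10% carried, against 95.7–96.1% for observed-only. With 20% carried the figures were 93.1–95.6% and 93.5–93.7%. No power gain is claimed.

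**The SAP's remark on ungradable scans gives no Week 16 SD-OCT rate.** It names OCTA as the main problem, and OCTA has left the primary analysis. That ungradable SD-OCT grades are skipped is itself a reasonable inference; the SAP states it explicitly as missing only for CNV type.

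**The change is not hidden.** LOCF is discussed openly among the protocol changes, with a reason. The protocol's complete-case rule is implied, not written, and its predictors were visit-specific values and not changes. This narrows the complaint about disclosure to one thing: the move from sensitivity to primary is not stated.

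**Observed-only models can be selective.** Where pathology makes scans ungradable, leaving those eyes out may bias the result. This stands, and limits how the added models should be read.

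**Conclusion.** The point holds as a gap in the plan, not as a demonstrated bias. Three things rest on the documents alone: LOCF changed role without that being stated, the carried scan falls at 4 and not 8 weeks after an injection on the nominal schedule, and no planned model shows the odds ratios without carried values. The effect is most direct for CST and the changed categories; a Stable label can also hide an unseen Week 16 change.

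The size cannot be determined from the documents. Under the assumptions shown, with 10–20% of values carried at random, a true odds ratio of 2.0 appears as about 1.67 to 1.99. With missingness differing by outcome, the range is 1.40 to 2.16. If few Week 16 scans are ungradable, or successive scans agree closely with little shift, the effect is small. The plan should let the reader see which case applies.

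**What to change.** 1. In SAP 6.3.1 add, as a sensitivity analysis, the one-variable and multivariable models using only eyes with a graded Week 16 value. Show their odds ratios beside those of the LOCF models.
2. Report the number of carried values for each predictor, by source visit (Week 4, 8 or 12) and by outcome group.
3. State in SAP 1.1 that LOCF for the SD-OCT predictors moved from a sensitivity analysis to the primary analysis.

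The cost is one more run of models already planned, one count table and a sentence of SAP text. The added models use fewer eyes and have somewhat wider intervals, as shown in the working. Because they can be selective when pathology prevents grading, they should be read beside the LOCF models and not replace them.

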12.4.2 Statistical model, hypothesis, and method of analysis

To test whether the above-mentioned anatomical parameters are predictors of response to brolucizumab in terms of fluid resolution and stable q12w regimen, participants within the Safety Set are to be divided in:

- q12w fluid-free participants, defined as participants who have maintained a stable q12w regimen up to Week 48 and are devoid of IRF and SRF at Week 48
- not q12w fluid-free participants, defined as participants who present IRF *or* SRF at Week 48 *or* have been on a q8w regimen at any time during the study *or* have dropped out at any time after Baseline

A Recursive Partitioning and Amalgamation (RECPAM) classification-tree analysis will be used to evaluate interactions between imaging measurements assessed by OCT, OCTA, FA, ICGA and CFP and to identify distinct and homogeneous subgroups of participants in terms of q12w fluid-free participants at Week 48.

This tree-based method integrates the advantages of main effects logistic regression and tree-growing techniques. At each partitioning step, the method chooses the covariate and its best binary split to maximize the difference in the outcome of interest. The algorithm stops when user-defined conditions (stopping rules) are met. To obtain more robust and stable splits, a permutation approach will be adopted to choose the best splitting variable. Global and local adjustment for possible confounders will be accounted for. Global variables will adjust the tree structure iteratively and add global coefficients to the model. Local variables will add different adjustment terms for any terminal node in a tree.

The RECPAM construction proceeds in the following three steps:

Step 1: Construction of a large tree.

Starting from the Safety Set (i.e. root node), the maximum dissimilarity between *q12w fluid-free patients vs non q12w fluid-free patients* for the Split Defining Statement (SDS) family (i.e. predictors variable) will be searched. This will identify the first branch of the tree and the corresponding tree. The same search will be performed recursively on the descendants of the root node, until a minimum node size specified by the user is reached. This defines the leaves of the larger tree.

Step 2: Pruning of the large tree and selection of the honest tree.

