The best tree will be select considering jointly the two criteria: the Akaike Information Criterion (AIC) and the simultaneous significance levels (SLn). According to the minimum AIC principle

(Akaike, 1974), the honest tree should be the tree of the pruning sequence having the smallest AIC. This criterion is justified by the asymptotic equivalence of the minimum AIC model choice and leave-one-out cross validation. According to the SL approach, on the other hand, we should choose the smallest tree such that SL_n is larger than a pre-fixed value, e.g. 0.05 or 0.01. Since the AIC sequence decreases, reaches a minimum and then increases with a characteristic jump in the increment, while SL sequence can only decrease but up to a point at which the SL drops rather abruptly, we will choose the point in which both curves show a characteristic elbow (Ciampi et al., 1995).

Step 3: Construction of the amalgamation tree and selection of the RECPAM classification.

For a given statistical significance α level, the leaves of the honest tree will be amalgamated successively until any couple of leaves is dissimilar at the nominal α level. This results in a sequence of nested partitions of the set of leaves of the honest tree, forming the amalgamation tree. The partition corresponding to the minimum AIC, is selected: it defines the RECPAM classification (Ciampi et al., 1991).

A multivariable logistic regression will then be applied to study the association between q12w fluid-free patients at Week 48 with different imaging parameters using the above-mentioned variables and the cut-off selected by the RECPAM analysis. FA, ICGA and CFP variables included in the model are measured at Screening, while OCTA and SD-OCT variables included in the model are assessed at Screening (only SD-OCT), Baseline and Weeks 4, 8, 12 and 16. The variables selection will be based on an automated stepwise selection.

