4. DEFINITIONS AND GENERAL METHODOLOGY

4.1. General Methodology

Statistical tables, listings and analyses will be produced using SAS® release 9.4 (64 bit) or later (SAS Institute, Inc., Cary, NC, USA).

The data from all sites will be pooled and summarized.

Continuous data will be summarized with mean, standard deviation (SD), median, Q1, Q3, minimum and maximum. Categorical data will be presented by absolute and relative frequencies (n and %) or contingency tables. The percentage calculation will be based on total values (i.e., count will be shown also in the missing category, unless otherwise specified).

Unless stated otherwise, a two-sided alpha level 0.05 will be considered. No alpha level adjustment will be carried out for primary and secondary outcome variables, unless otherwise specified.

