4.5. Multiple Comparison/Multiplicity

Not applicable.

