NA=Not Applicable; CNV=Choroidal Neovascularization; UNG/P=Ungradable due to pathology; UNG/Q=Ungradable due to quality SHRM=Subretinal hyper reflective materia; ORT=Outer retinal tubulation; ELM=External Limiting Membrane; CST=Center Subfield Thickness; PED=Pigment Epithelial Detachment.

Of note, for each variable 'Missing' values can be present in case that images are collected but not graded by Central Reading Center (CRC) since they are collected by means of a not certificated instrument.

| | |
|--|----------------------------------|
| | Statistical Analysis Plan |
| | Sponsor: Novartis |
| | Protocol: CRTH258AIT04 |

Analysis methodology

Firstly, the proportion of patients with and without q12w fluid-free will be provided and then a descriptive summary table by q12w fluid-free and not q12w fluid-free will be provided for each variables described in table above.

A logistic models will be performed for each one of the variables listed above considering as outcome the patients' classification in q12w fluid-free and not q12w fluid-free.

Multivariable logistic model will be performed considering as outcome the patients' classification in q12w fluid-free and not q12w fluid-free and as covariates all the variables with $p<0.10$ in the previous analysis. Results of logistic models will be presented in terms of beta coefficient and standard error, Odds Ratio and relative 95% Confidence interval and p-value.

All these analyses will be performed on Safety population.

Data handling rules

In case of patients who dropped out at any time after baseline, the primary outcome cannot be evaluated since the patient status related to treatment regimen and presence of IRF o SRF at Week 48 are not observed. The dropped-out patients constitute intercurrent event and they will be considered a not q12w fluid-free at Week 48. Similarly, in case of patients who discontinued the treatment at any time after baseline, the primary outcome cannot be totally evaluated since the patient treatment regimen at q12w cannot be observed until Week 48. The patients who discontinued treatment constitute intercurrent event and they will be considered a not q12w fluid-free at Week 48.

Sensitivity of primary analysis

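### The primary analysis tests seven candidate predictors, refits those with p<0.10 on the same patients, and reports unadjusted, post-selection p-values and confidence intervals as ordinary 5% inference

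*SAP*

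**What the plan says.** SAP 6.3.1 lists seven variables that "will be considered as potential predictive factors in the statistical model": predominant CNV lesion type, sub-RPE fluid, SHRM, outer retinal tubulation, ELM integrity loss, type of PED, and percentage change in CST. The analysis then has two stages on the Safety population. First, "A logistic models will be performed for each one of the variables listed above". Second, a multivariable logistic model takes "as covariates all the variables with $p<0.10$ in the previous analysis". Results are presented as coefficients with standard errors, odds ratios with 95% confidence intervals, and p-values.

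SAP 4.1 sets the level ("Unless stated otherwise, a two-sided alpha level 0.05 will be considered") and adds: "No alpha level adjustment will be carried out for primary and secondary outcome variables, unless otherwise specified". SAP 4.5, on multiplicity, reads in full: "Not applicable". The only sensitivity analysis in SAP 6.3.1 is an inverse-probability-weighted refit with the covariates already selected.

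The SAP does not say whether p<0.10 means the overall test of a multi-category variable or any one of its coefficients, nor whether the test is Wald or likelihood-ratio. Neither document calls the primary analysis exploratory.

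**The concern.** The primary objective is to name the early parameters that predict a q12w fluid-free response, and Protocol 1.2 says their use is to support the choice between q12w and q8w. Seven chances to find a predictor, each read at 5%, do not give a 5% error rate for that conclusion.

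In addition, the model-based intervals and p-values of the multivariable model assume that its covariates were fixed in advance. Here each covariate is present because it already showed p<0.10 in the same patients. The weighted refit reuses those covariates, so it cannot reveal a selection error. A chance association could therefore be reported as a biomarker, with an interval that looks convincing and an odds ratio that is too large.

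**Working it through.** **The plan's own figures.** The documents give no false-selection rate; their sample-size figures concern the precision of the responder proportion, and they reproduce.
- Protocol 12.7.1: n = 4 × 1.96² × 0.56 × 0.44 / 0.12² = 262.9, so 263.
- SAP 3.5: width at N=122 and p=0.50 is 2 × 1.96 × √(0.25/122) = 17.74%.

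**Inputs.** Seven variables, threshold 0.10 and level 0.05 (SAP 6.3.1 and 4.1); N=122 (SAP 1.1); responder rate 46–56% (SAP 3.5). With Type I and PCV merged, lesion type has three categories, five variables have four, and CST is continuous: 2 + 5×3 + 1 = 18 coefficients.

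**Closed form, seven independent null predictors.**
- At least one passes p<0.10: 1 − 0.9^7 = 52.2%.
- At least one p<0.05 among seven unscreened tests: 1 − 0.95^7 = 30.2%.
- At least one p<0.05/7: 1 − (1 − 0.00714)^7 = 4.9%.

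**Null simulation of the two-stage rule.** Assumptions not in the documents: category frequencies (for example 0.30/0.30/0.25/0.15 or 0.45/0.25/0.25/0.05), predictor correlation 0 or 0.3, and N=90 as an alternative number with usable images. The ranges span several sets of scenarios.

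| p-value read | Model non-empty | Any p<0.05 in final model |
|---|---|---|
| Joint likelihood ratio throughout | 53–59% | 28–35% |
| Joint likelihood-ratio screen, joint Wald in final model | 51–58% | 16–25% |
| Joint Wald throughout | 37–50% | 14–25% |
| Any single coefficient | 74–84% | 30–58% |

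In round terms, overall tests give 40–58% for a non-empty model and 15–35% for a p<0.05 predictor. At an assumed N=80, joint Wald tests give a non-empty model in 31–44%.

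**Source of the inflation.** Seven one-variable tests at 0.05 with no screening gave any p<0.05 in 32–36% (likelihood ratio) or 16–23% (Wald). The two-stage rule gave 28–35% and 14–25%. Screening and refitting therefore do not raise the familywise rate materially; the number of unadjusted tests does.

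**What selection does to the estimates.** Take one null predictor that enters alone.
- A null p-value is uniform, so P(p<0.05 given p<0.10) = 0.05/0.10 = 50%. The 95% interval then covers 1 about 50% of the time. Simulation for a continuous predictor such as CST at N=122 gave 53–55%.
- The standard error of the log odds ratio per SD is about 1/√(122 × 0.25) = 0.181. The mean |z| given |z|>1.645 is 2 × 0.1031/0.10 = 2.06. The typical reported odds ratio, folded above 1, is then exp(0.181 × 2.06) = 1.45; simulation gave 1.49. The true value is 1.

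**The case against.** Several objections are sound.

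- **Entry is not a claim.** A reader might infer that the plan falsely names a predictor about half the time. The documents do not support that: p<0.10 is an entry threshold, and no section equates entry with an identified predictor. The relevant rate is the 15–35%. Nor is a non-empty model always more likely than not; under joint Wald tests it is at or below half.
- **Screen-and-refit is not the cause.** A reader might blame the two-stage rule for the familywise inflation. The comparison with unscreened tests shows otherwise.
- **The protocol was no safer at the end.** A reader might infer that the SAP discarded the protocol's safeguards and put nothing in their place. Protocol 12.4.2 did include AIC and simultaneous-significance pruning, and "a permutation approach will be adopted to choose the best splitting variable". But those governed the RECPAM tree. The protocol also finished with an ordinary logistic model on the same patients, using data-derived cut-offs and automated stepwise selection, with no adjustment specified. The SAP searches less: no cut-off search, no stepwise step, no OCTA predictors, and one pre-defined summary per repeated measure.
- **The global null is severe.** Response requires staying on q12w, and investigators may use sub-RPE fluid and CRT to choose the regimen, so some association for sub-RPE fluid and CST is expected by design. Leaving those two out, five null candidates still give 1 − 0.95^5 = 22.6% and 1 − 0.9^5 = 41.0%.
- **Setting.** This is a single-arm phase IV study sized for precision, and non-adjustment is stated openly. That lowers the stakes but does not make the reported intervals correct, and the documents do not present the primary result as exploratory.

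**Conclusion.** The point holds. With no true predictor, the chance of at least one p<0.05 in the final model is roughly 15–35% on overall tests, three to seven times the nominal 5%. This comes from testing seven variables without adjustment. Separately, selection makes the reported estimates unreliable: for a null variable selected alone, a nominal 95% interval has coverage of about one half, and the odds ratio is about 1.45–1.49 per SD for a continuous predictor.

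The 52% and 50% figures are arithmetic under independence and uniform null p-values. The simulated ranges rest on assumed category frequencies and correlations, and on the choice of test, which the SAP leaves open. Reading single coefficients instead of joint tests would make the rates higher, up to 58% for any p<0.05.

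**What to change.** Keep the multivariable logistic model, which Protocol Table 12-1 names as the method for the primary estimand. Resting the primary claim on one-variable tests instead would displace it and could not show independent prediction. In the SAP:

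1. State in 6.3.1 that the p-values and confidence intervals of the multivariable model are post-selection and descriptive.
2. Specify in 6.3.1 that p<0.10 applies to the joint test of each variable, and name that test (likelihood-ratio or Wald).
3. Report familywise-adjusted p-values for the seven one-variable joint tests beside the unadjusted ones, by Holm or a min-p permutation test: shuffle the response labels, rerun all seven models, and compare each observed p-value with the distribution of the smallest. Permutation is preferable at this N, because Bonferroni on likelihood-ratio tests still gave about 8% in simulation.
4. Replace the entry in 4.5 with this rule; the exception clause in 4.1 already allows it.

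The cost is a short extra program and no new data. Fewer parameters will be significant after adjustment. For one continuous predictor at N=122, Bonferroni (the first Holm step) lowers simulated power from 96% to 82% at an odds ratio of 2.0 per SD, and from 59% to 30% at 1.5. The unadjusted results stay in the report.
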